#### **8.7.4.1. Time-to-Event Analyses**

The time to occurrence of the following endpoints will be also analyzed at both the primary and final analyses:

- First confirmed 40% reduction in eGFR, ESRD, or death
- Initiation of systemic immunosuppressive medication (all and renal indication only)

Time-to-event data will be analyzed using a Cox regression model, stratified by randomization strata, via PROC PHREG in SAS. The tabulation will also include the KM estimates of the medians and corresponding 95% CIs if the medians can be estimated. The number and percent of patients censored and with events will be presented. Patients without any documentation of events will be censored at the time of analysis (if still on randomized treatment) or the time of discontinuation of randomized treatment, whichever is earlier.

For patients with an event for the first confirmed 40% reduction in eGFR, ESRD, or death endpoint, the minimum of the following event dates will be used:

- Death
  - Date of death
- ESRD
  - Date of initiation of RRT
  - Date of first occurrence of eGFR  $<15$  mL/min/1.73 m^2 (confirmed after repeat assessment of at least 14 days after initial assessment)
- Confirmed 40% reduction from baseline in eGFR
  - Date of first assessment meeting criteria

Reduction of eGFR requires confirmation by a value at least 4 weeks after the initial value. If a patient experiences more than one of these events, only the event that occurs first will be included in the analysis.

Additional sensitivity analysis may be performed at final analysis if there are sufficient events after premature treatment discontinuation during the double-blind period.

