The following endpoints, considered as simple binary outcomes, will be analyzed using a logistic regression analysis with a fixed effect for randomized treatment and baseline eGFR included as a covariate. The analysis will be stratified by the randomization strata. The treatment effect estimate from the model will be the contrast between sparsentan and irbesartan log odds. The treatment effect estimate, and its 95% CI will be back-transformed to provide results on the odds ratio scale, and the associated two-sided p-value will be presented as follows:

- The proportion of patients achieving a urinary protein excretion of  $<0.3$  g/day up to Week 110.
- The proportion of patients achieving a urinary protein excretion of  $<1.0$  g/day up to Week 110.
- The proportion of patients requiring systemic immunosuppressive medication during the study.
- The frequency of hospitalizations (for any reason and for reasons related to the kidney).

The proportion of patients reaching a confirmed 40% change from baseline in eGFR, ESRD, or death will be analyzed via PROC PHREG in SAS in terms of the time to the first of a confirmed 40% change from baseline in eGFR, ESRD, or death using a Cox regression model stratified for the randomization stratification factors and with a fixed effect term for randomized treatment. The hazard ratio along with its 95% CI and two-sided p-value will be provided. The data will also be displayed by randomized treatment group using Kaplan-Meier estimates of the cumulative density function.

The use of systemic immunosuppressive medication and the frequency of hospitalizations will also be analyzed in terms of the number of systemic immunosuppressive medications and the

number of hospitalizations for any reason per patient, using a Negative Binomial regression model via PROC GENMOD in SAS. The model will be stratified for the randomization stratification factors and will include a fixed effect term for randomized treatment. The analyses will be adjusted for duration of exposure to randomized treatment. Estimated event rates will be extracted from the model for each randomized treatment. The treatment effect will be presented as the ratio of event rates together with the associated 95% CI and two-sided p-value.

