#### 4.4. Randomization

Randomization will be carried out using an interactive response technology (IRT) system, with central randomization following a 1:1 ratio between the 2 treatment arms, based on a permuted-block randomization method. Randomization will be stratified by the following factors:

- eGFR value at Screening (30 to <60 mL/min/1.73 m^2 and ≥60 mL/min/1.73 m^2)
- Urine protein excretion at Screening (≤1.75 g/day and >1.75 g/day)

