#### **8.4.3. Procedure for Testing Other Secondary Endpoints Within the US and Non-US Countries**

At the time of the final (confirmatory) analysis, if all the key secondary endpoints achieve statistical significance within the US or non-US countries, the other secondary endpoints will be statistically tested at the available alpha in the order specified below:

1. The mean change from baseline in UP/C at Week 110
2. The mean change from baseline in urine protein excretion at Week 110
3. The mean change from baseline in UA/C at Week 110
4. The mean change from baseline in urine albumin excretion at Week 110
5. The proportion of patients reaching a confirmed 40% reduction in eGFR, ESRD, or death
6. The mean change from baseline in eGFR at Week 110

The multiple testing strategies for the US and for non-US countries are shown in [Figure 1](#).

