## 8.5. Analysis of the Primary Efficacy Endpoint

### 8.5.1. Primary Efficacy Analysis

The primary efficacy analysis will be based on the PAS (at primary analysis) and FAS (at final analysis) and change from baseline (Day 1) in proteinuria (UP/C) will be analyzed via an MMRM analysis. The dependent variable will be UP/C change from baseline. As UP/C is a highly right-skewed variable, analyses will be performed on log-transformed data. The model will include the following fixed effects:

- Treatment group (2 levels: sparsentan, irbesartan)
- Baseline UP/C in log scale
- Time (ie, analysis visit in weeks)
- Treatment group by time interaction
- Randomization stratification variable (4 levels based on Screening eGFR and urine protein excretion)

In addition, patient will be included as a random effect.

Under the assumption of MAR, missing data will be imputed using the MI procedure (Ouyang 2017; Rubin 1987) for the UP/C result in the natural log scale. Specific imputation procedures are provided in [Section 6.6.1.1](#).

An unstructured covariance matrix will be used. If the computational algorithm fails to converge, the following structures will be executed: heterogeneous Toeplitz, heterogeneous Compound Symmetry, heterogeneous first-order autoregressive, Toeplitz, Compound Symmetry, and first-order autoregressive.

The treatment effect will be the contrast between sparsentan and irbesartan LS means at Week 36. The LS means, treatment effect estimate (difference in LS means), 95% CI, and 2-sided p-value will be extracted from the model. Results will be back-transformed to present treatment effects on the ratio scale.

Estimates and CIs will be converted to percentages via the following transformations:

$$[\exp(\text{LS mean change from baseline in natural log(UP/C)}) - 1] \times 100$$

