### **8.7.4. Other Responder Endpoints**

Responder endpoints will be summarized at both the primary and final analysis. For these responder endpoints, patients are classified as either a responder or a non-responder.

The following endpoints will be analyzed via a logistic regression model with a fixed effect for treatment and baseline eGFR (baseline urinary protein excretion for complete remission defined as urinary protein excretion <0.3 g/day, partial remission defined as urinary protein excretion <1.0 g/day) as a covariate, stratified by the randomization strata:

- The proportion of patients reaching a confirmed 40% reduction in eGFR, ESRD, or death
- The proportion of patients achieving urinary protein excretion <0.3 g/day up to Week 110

- The proportion of patients achieving urinary protein excretion  $<1.0$  g/day up to Week 110

The treatment effect estimate from the model will be the contrast between sparsentan and irbesartan log odds. The treatment effect estimate and its 95% CI will be back-transformed to provide results on the odds ratio scale, and the associated 2-sided p-value will be presented.

Reduction of eGFR requires confirmation by a value at least 4 weeks after the initial value. If the last value on randomized treatment is the initial value for reduction or eGFR  $<15$  mL/min/1.73 m^2, then the last value on randomized treatment is considered confirmed or sustained. ESRD is defined as initiation of RRT or sustained eGFR  $<15$  mL/min/1.73 m^2 during the study (confirmed after repeat assessment of at least 14 days after initial assessment).

The following endpoint will be analyzed using a generalized mixed model repeated measure analysis using PROC GLIMMIX in SAS:

- Proportion of patients with hematuria at each visit as determined by presence of blood in urinalysis
- Proportion of patients with use of systemic immunosuppressive medication during each 12-week time bucket.

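### The models for the kidney composite leave within-stratum baseline eGFR and proteinuria unused; the planned Cox test is valid but may give up some power

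*SAP*

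**What the plan says.** SAP 8.7.4.1 specifies the time-to-event analysis: "Time-to-event data will be analyzed using a Cox regression model, stratified by randomization strata, via PROC PHREG in SAS". It lists no covariate. Protocol 12.7.4 gives the same model for this composite, a "Cox regression model stratified for the randomization stratification factors and with a fixed effect term for randomized treatment".

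SAP 8.7.4 also analyses the composite as a yes/no outcome, by a "logistic regression model with a fixed effect for treatment and baseline eGFR", stratified by the randomization strata. Baseline urinary protein excretion is the covariate only for the two remission endpoints in that section.

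The strata are four cells formed from screening eGFR (30 to <60, or ≥60) and screening urine protein excretion (≤1.75 or >1.75 g/day), per SAP 4.4.

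SAP 8.4.3 places the composite fifth of six other secondary endpoints tested in fixed order once all key secondaries succeed. It is worded as "The proportion of patients reaching a confirmed 40% reduction in eGFR, ESRD, or death", with no model named. SAP 8.7.4 lists the logistic model first and 8.7.4.1 introduces the Cox analysis as an addition, whereas Protocol 12.7.4 assigns the endpoint to Cox.

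**The concern.** Each stratifier is a single cut on a wide range. Entry requires eGFR of at least 30 and protein excretion of at least 1.0 g/day, with no upper limit on either (Protocol 7.1.1), so patients with very different values share a cell. Stratifying on these two variables implies that the sponsor expects them to be prognostic, and both are measured before treatment.

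Elsewhere the SAP adds a continuous baseline value on top of the strata: the UP/C model (8.5.1), the eGFR slopes (8.6.1, 8.6.2) and the Week 114 analysis (8.7.2). For this composite it adjusts for continuous eGFR in the logistic model but not in the Cox model, and gives no reason.

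At stake is some power for the only clinical-event endpoint in the controlled sequence, and for item 6 (change in eGFR at Week 110), the one endpoint behind it.

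**Working it through.** **No figure of the plan's own.** SAP 4.3.1 and Protocol 12.2 size the trial on UP/C and eGFR slope. They state no event count or power for this composite, so there is nothing to reproduce.

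**Inputs from the documents.** About 380 patients, 1:1 allocation, the four strata as above, two-sided alpha 0.05. (For non-US countries the available alpha is 0.04 if the 6- to 58-week slope test fails. That level was not simulated.)

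**Assumptions not in the documents.** True hazard ratio 0.5; control-arm risk over the treatment period of 15%, 25% or 35%; 15% dropout; exponential event times; assumed covariate distributions; the same prognostic strength for both covariates. Strength is the hazard ratio per SD of lower eGFR and per SD of higher log urine protein: 1.35 (weak), 1.82 (moderate) or 2.46 (strong). Strata were cut from the same values used as covariates.

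**Scale.** The Schoenfeld formula, 4(1.960 + 1.282)²/(ln HR)², gives 42.03/0.480 = 87.5, so 88 events for 90% power at HR 0.5. The simulated trials averaged about 40 to 42, 67 to 71 and 96 to 102 events at the three risks.

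**Cox power (%), 1000 simulated trials per setting: planned (strata only) → strata plus both continuous covariates**

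| Prognosis (HR per SD) | 15% risk | 25% risk | 35% risk | Gain (points) |
|---|---|---|---|---|
| Weak (1.35) | 55.3 → 56.1 | 79.0 → 79.1 | 90.9 → 91.8 | 0.8, 0.1, 0.9 |
| Moderate (1.82) | 53.4 → 55.3 | 79.1 → 81.8 | 89.0 → 92.6 | 1.9, 2.7, 3.6 |
| Strong (2.46) | 51.1 → 57.3 | 70.4 → 79.8 | 83.2 → 91.8 | 6.2, 9.4, 8.6 |

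With no prognostic effect the change was between −0.2 and +0.4 points. The Monte Carlo standard error is about 1 to 1.6 points per figure; the models were fitted to the same data, so differences are more precise.

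**Source of the gain.** In the strong case, adding eGFR alone took power to 52.2%, 72.0% and 84.6%, a gain of 1.1, 1.6 and 1.4 points. Log protein supplied the remaining 5.1, 7.8 and 7.2.

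**What the strata already recover.** In the strong case the unstratified Cox model had 48.2%, 63.8% and 76.7% power. The planned strata recover (51.1 − 48.2)/(57.3 − 48.2) = 32%, (70.4 − 63.8)/(79.8 − 63.8) = 41% and (83.2 − 76.7)/(91.8 − 76.7) = 43% of the gap to full adjustment.

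**Logistic power (%), strata plus eGFR → with log protein added.** At 15%, 25% and 35% risk:
- Weak: 56.1 → 56.8, 79.0 → 79.4, 90.9 → 90.8
- Moderate: 53.8 → 55.1, 77.7 → 79.1, 87.7 → 89.9
- Strong: 52.1 → 55.7, 71.4 → 74.9, 81.4 → 85.5

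The gain runs from about 0 to 4 points.

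**Type I error** (no treatment effect, 25% risk, 2000 runs, standard error about 0.5 points; no prognosis and strong prognosis respectively). Planned Cox: 5.1% and 5.6%. Adjusted Cox: 5.5% and 4.9%. Logistic: 5.2% and 5.9% as planned, 5.1% and 6.2% with log protein. The strong-case logistic figures run slightly high with or without the added term.

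**Shift in the estimate.** In the strong case at 25% risk the median log hazard ratio moves from −0.609 (HR 0.54) with strata only to −0.699 (HR 0.50) with both covariates.

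**The case against.** A Cox model stratified by the randomization factors is a standard, valid, pre-specified analysis, so the choice can be called one of preference. Several stronger readings that a reader might infer do not survive:

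- **That baseline prognosis is ignored.** Screening eGFR and protein excretion enter both models through the strata, and the logistic model also has continuous eGFR. Only within-stratum variation is lost.
- **That the Cox p-value is the controlled one.** The SAP does not settle this. If the logistic model is the test, the possible gain is only about 0 to 4 points.
- **That much of the sequence depends on the composite.** It is reached only after all key secondaries and items 1 to 4 succeed, and only item 6 follows it.
- **That the planned hazard ratio is wrong because it lies nearer 1.** The adjusted hazard ratio is a different, conditional quantity.
- **That few events make the loss worse.** In the strong case the gain was smallest at the lowest event rate.

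Two further points against the concern have force. The only hazard ratio in the documents, 0.36, is for a different composite (creatinine doubling, ESRD or death). At that effect about 41 events give 90% power (42.03/1.044 = 40.3), leaving less to gain. Also, the SAP's pattern is to adjust for the outcome's own baseline: the slope models carry baseline eGFR but no UP/C. Consistency therefore supports adding eGFR to the Cox model, while the case for proteinuria rests on its expected prognostic value. Most of the simulated gain comes from that second term.

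The preference argument does not dispose of the point. The SAP treats the same composite differently in its two models without explanation, and adjustment cost no more than 0.2 points of power in any setting run.

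**Conclusion.** The concern holds as a matter of efficiency. The Cox model for the composite uses baseline eGFR and proteinuria only as two-level screening strata, and the logistic model lacks continuous baseline proteinuria. The planned Cox test is valid; nothing here suggests a wrong or conservative error rate.

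The Cox gain from adding both covariates is about 0 to 1 point under weak prognosis, 2 to 4 under moderate and 6 to 9 under strong. The logistic gain from adding log proteinuria is about 0 to 4. These figures rest on an assumed hazard ratio of 0.5, control risk of 15% to 35%, 15% dropout, assumed covariate distributions and equal prognostic strength, none of which the documents supply. The gain could be negligible. A cheap improvement is worth making, but this is not a defect in the test. The unnamed confirmatory model for item 5 should be resolved in the same edit.

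**What to change.** - In SAP 8.7.4.1 and Protocol 12.7.4, add continuous baseline eGFR and log baseline UP/C to the Cox model for the composite, keeping the stratification.
- In SAP 8.7.4, add log baseline UP/C to the logistic model for this composite. Log baseline UP/C is already a covariate in the primary model. Urine protein excretion could serve instead, but one measure must be named in advance.
- In SAP 8.4.3, state whether the Cox or the logistic model gives the p-value for item 5.

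The change should be made before final unblinding, by people who have not seen unblinded composite results, because SAP 8.7.4.1 also runs this analysis at the primary analysis.

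The cost is a few sentences, no new data, and two added parameters in the Cox model and one in the logistic. The downside is that the hazard ratio or odds ratio becomes conditional on the covariates and must be labelled so.

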#### **8.7.5. Analyses of Events Rates**

The following efficacy endpoints, considered event rate endpoints, will be analyzed using a negative binomial regression model, via PROC GENMOD in SAS:

- Number of systemic immunosuppressive medications over the treatment period
- Number of days treated with systemic immunosuppressive medications
- Number of hospitalizations (for any reason and for reasons related to the kidney)

Specifically, the model will compare treatment groups, adjusted for the randomization stratification factors, and will include the natural log transformation of duration of exposure as an offset term. Estimated event rates will be extracted from the model for each treatment. The treatment effect will be presented as the ratio of event rates, along with the associated 95% CI and 2-sided p-value.

## **9. PHARMACOKINETICS**

The PK Analysis Set will be used for all PK analyses. Trough plasma PK concentrations of study medication will be summarized at both the primary and final analyses with descriptive statistics over time by treatment group, including the geometric mean and geometric CV%. Analyte concentrations below the lower limit of quantification will be indicated by below limit of quantification (BLQ) and set to missing.

However, the number of BLQs at each time point will be provided in the summary table.

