### **12.9.2. Pharmacokinetics**

Trough plasma levels for sparsentan and irbesartan will be summarized by visit using descriptive statistics.

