### 3.2.2. Exploratory Endpoints – Double-Blind Period

Exploratory endpoints are listed below:

- The rate of change in eGFR over a 58-week (approximately 1-year) period following the initiation of randomized therapy (thus, the analysis is from Day 1 to 58 weeks post randomization; eGFR total slope at 1 year)
- The change from baseline in eGFR at 6 weeks post randomization (ie, the acute effect of randomized therapy)
- The change from end of treatment (EOT, ie, Week 110) in eGFR 4 weeks following cessation of treatment (ie, at Week 114)
- Change in eGFR from baseline to 4 weeks post cessation of randomized treatment (Week 114)
- Achievement of urinary protein excretion of <0.3 g/day up to Week 110
- Achievement of urinary protein excretion of <1.0 g/day up to Week 110
- The proportion of patients with hematuria at each visit
- Changes from baseline in blood pressure at each visit
- The proportion of patients requiring systemic immunosuppressive medication during the study
- Mean changes from baseline in quality of life (QoL), measured via patient-reported outcome (PRO) at each visit
- Frequency and duration of hospitalizations (for any reason and for reasons related to the kidney)
- Trough plasma pharmacokinetic (PK) concentrations

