### **6.2. Data Conventions**

The precision of original measurements will be maintained in summaries, when possible.

For tables where rounding is required, rounding will be done at the final stage of the calculation to the nearest round-off unit. For example, when rounding to the nearest integer, values  $\geq XX.5$  will be rounded up to  $XX + 1$  (eg, 97.5 will round up to 98), while values  $< XX.5$  will be rounded down to  $XX$  (eg, 97.4 will round down to 97).

Percentages based on frequency counts will be based on available data, and denominators will generally exclude missing values, unless otherwise stated. For frequency counts of categorical variables, categories whose counts are zero will be displayed for completeness. For example, if

none of the patients discontinued due to “lost to follow-up,” this reason will be included in the table with a count of 0. Percentages based on frequency counts of case report form (CRF) collections (eg, demographic categories) will be presented as a whole number (no decimal places), and nonzero values less than 0.5% will be presented as “<1%.” Values less than 100% but that round up from 99.5% to 100% will be presented as “>99%.”

Quantitative laboratory tests containing less than (<) and greater than (>) symbols are test results that are below and above quantifiable limits, respectively. In order to retain these values for analysis purpose, values will be imputed as the numeric portion of the result.

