#### **6.3.5. Pharmacokinetic Analysis Set**

The PK Analysis Set includes all patients who have received at least 1 dose of study medication and have at least 1 confirmed, fasted, and analyzable sample. Patients must have been fasting for approximately 8 hours before the visit and must not have had any major protocol deviations that potentially affect exposure levels. The PK Analysis Set will be used for PK analyses.

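### By-visit trough statistics in SAP 9 describe only samples with quantifiable drug, because results below the assay limit are set to missing; the median and quartiles could keep them at almost no cost

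*SAP*

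**What the plan says.** SAP 3.2.2 lists "Trough plasma pharmacokinetic (PK) concentrations" among the exploratory endpoints of the double-blind period. Protocol 12.9.2 plans nothing beyond description: "Trough plasma levels for sparsentan and irbesartan will be summarized by visit using descriptive statistics".

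SAP 9 restricts the PK analyses to the PK Analysis Set and summarizes troughs at both the primary and the final analysis with "descriptive statistics over time by treatment group, including the geometric mean and geometric CV" (as a percentage). On low results it says: "Analyte concentrations below the lower limit of quantification will be indicated by below limit of quantification (BLQ) and set to missing". It then adds: "However, the number of BLQs at each time point will be provided in the summary table".

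SAP 6.3.5 requires each patient in the PK Analysis Set to "have at least 1 confirmed, fasted, and analyzable sample" and to have no major protocol deviation that could affect exposure. SAP 7.3 lists what evaluability for that set rests on, including no extended dosing interruptions and compliance within 80% to 120%.

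SAP 6.2 has a general convention for laboratory results outside the quantifiable range: "Quantitative laboratory tests containing less than (<) and greater than (>) symbols are test results that are below and above quantifiable limits, respectively". It continues: "In order to retain these values for analysis purpose, values will be imputed as the numeric portion of the result".

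**The concern.** A BLQ trough on planned daily dosing is information: at that moment the patient had little or no measurable drug. The schedules of events (Protocol Tables 15.1-1 and 15.1-2) mark PK samples at Weeks 6, 12, 36, 48, 70, 94 and 110 and none at Day 1, so by the schedule a BLQ result is not an expected zero before first dosing.

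Setting such results to missing removes the low end of the distribution before the statistics are computed. Each statistic then answers a narrower question, namely how high the trough was where drug could be measured, and the section does not say so. A reader of the table is likely to take the median or geometric mean as the typical trough of the patients sampled. At stake is the accuracy of a descriptive exposure table: averages that are somewhat high and a spread that is somewhat narrow.

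**Working it through.** **Inputs.** The documents state no assay limit, no expected BLQ share, no variability of troughs and no PK sample count. There is no planned figure to reproduce. What follows fixes the direction, then shows the size under assumptions labelled as such.

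**Direction.** At one visit let n samples be quantifiable and b be BLQ, with p = b/(n+b). Every BLQ value lies below every quantifiable value. Removing the b lowest values raises the mean and the geometric mean and cannot lower the median. The reported median is the all-sample quantile p + (1−p)/2 = (1+p)/2, which is the 52.5th percentile at p = 5% and the 55th at p = 10%. The reported lower quartile is the all-sample quantile p + (1−p)/4 = (1+3p)/4, which is the 32.5th percentile at p = 10%.

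**Size, assumption A: lognormal troughs with the assay limit at the p-th quantile.** Let s = √ln(1+CV²), where CV is the geometric CV, let q be the standard normal p-quantile, and let φ be the standard normal density.

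- Geometric mean with BLQ dropped, relative to the true value: exp(s·φ(q)/(1−p)). Example with CV 100% and p = 5%: s = 0.833, φ(q)/(1−p) = 0.103/0.95 = 0.109, exp(0.833 × 0.109) = 1.095.
- Geometric mean with BLQ set to the limit (the SAP 6.2 convention), relative to the true value: exp(s·[φ(q) + p·q]).

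The ranges below are for CV 50% to 150%.

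| Assumed BLQ share | Geometric mean too high, BLQ dropped | Geometric mean too high, BLQ at limit | True geometric CV of 100% reads as (BLQ dropped) |
|---|---|---|---|
| 1% | 1% to 3% | 0.2% to 0.4% | 96% |
| 5% | 5% to 13% | 1% to 2% | 87% |
| 10% | 10% to 24% | 2% to 5% | 80% |
| 20% | 18% to 46% | 5% to 13% | 71% |

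**Size, assumption B: BLQ samples contain essentially no drug.** Against zeros, the arithmetic mean is too high by 1/(1−p) − 1, that is 1%, 5%, 11% and 25% at p = 1%, 5%, 10% and 20%. A geometric mean cannot take zeros, so it can only be compared with a substitute. Against substitution at the limit the ratio is r^p, where r is the geometric mean of the quantifiable samples divided by the limit. At p = 5% this gives 12% for r = 10 and 26% for r = 100. The answer depends on r, which is unknown.

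**How BLQ samples can arise.** Under Protocol 6.3.1, patients who interrupt drug temporarily keep attending visits. Two things limit this route. No PK samples are taken once the end-of-treatment visit is completed (footnotes to Tables 15.1-1 and 15.1-2), and SAP 7.3 screens the PK Analysis Set for extended interruptions and for compliance. The screen is not complete: the 80% bound still admits a patient who misses up to one capsule in five (1 − 0.80 = 0.20), and short interruptions are not excluded. The sample requirement in SAP 6.3.5 works per patient, so it does not by itself remove single BLQ samples.

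**The case against.** The case for leaving the rule alone has several parts.

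- **The exclusion is disclosed.** The BLQ count stands in the same table. With n, b and a substitute value x, a reader can rebuild the mean as (n·mean + b·x)/(n+b) and the geometric mean as GM^(n/(n+b)) · x^(b/(n+b)). This stands for those two statistics, given the assay limit. It does not stand for the median and quartiles, which need the individual values. The patient listings (Protocol 12.1, SAP 6.1) would supply them, but only by redoing the table.
- **The target is a choice.** A sample taken during an interruption is not the trough of a dosing interval, so reporting quantifiable troughs and counting the rest separately is coherent. SAP 10.2 also summarizes interruptions and compliance. This stands, which is why upward bias is claimed only for a summary of all troughs, and why labelling is part of the fix.
- **The analysis set screens out the main source.** SAP 7.3 removes most prolonged non-exposure. This stands and makes a small effect more likely.
- **Nothing is decided on it.** The endpoint is exploratory, appears nowhere in the testing order of SAP 8.4 and enters no power calculation. This stands.

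Two stronger readings are tempting. A reader might infer that a real fall in exposure over 110 weeks could be hidden behind flat averages. The documents do not support that: a growing undetectable share would appear as a rising BLQ count at each visit, and the analysis set limits accumulating interruptions. A reader might also infer that the SAP contradicts itself, because section 6.2 keeps low laboratory results. Section 6.2 is a general convention and section 9 a specific one with its own flag and count. The difference is unexplained, but there is no doubt about which rule governs PK.

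**Conclusion.** The point holds in a limited, conditional form. The rule in SAP 9 makes every by-visit trough statistic conditional on quantifiable drug. If any samples are BLQ, the mean and geometric mean are biased upward as a summary of all troughs, the median cannot be too low, and under the lognormal assumption the geometric CV% is too small. The count discloses this without correcting it.

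The size is unknown. The percentages in the working depend on an assumed BLQ share and on an assumed variability (A) or ratio to the limit (B), so none should be quoted as the error in this trial. With no BLQ samples the error is zero. Given the analysis-set criteria and the exploratory, descriptive status of the endpoint, this is a minor improvement to reporting with no bearing on the efficacy conclusions.

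**What to change.** In SAP 9:

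1. Compute the by-visit median and quartiles with BLQ samples kept and ranked below all quantifiable values. No substitute value is needed. The median is a number as long as fewer than half the samples are BLQ, and the lower quartile as long as fewer than a quarter are; otherwise print BLQ.
2. Keep the BLQ count at each time point.
3. Label the mean, geometric mean and geometric CV% as based on quantifiable samples only.
4. Optionally, add a geometric mean with a stated positive substitute as a sensitivity summary, for example the limit itself (as in SAP 6.2) or half of it. The result depends on that choice, so it should not replace the median.

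The cost is a sentence or two in the SAP and a small programming change. Nothing now planned is lost, and no other analysis is touched.
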